# Inverse Probability Weighting (IPW; Secondary Objectives)

Do not distribute for purposes outside of specific activities related to development of FDAMAs114 compliant pieces. Content within this protocol is subject to change based on communication planning and input by external review committees.

Pfizer Confidential

Page 28 of 37

Apixaban NON-INTERVENTIONAL STUDY PROTOCOL

IPW uses propensity scores to obtain estimates of the average treatment and censoring effect. Propensity scores will be calculated using repeated measures logistic models with: 1) ever-treated with OAC and never-treated with OAC cohorts; 2) each DOAC treated and never-treated with OAC cohorts included in the model, using never-treated patients as the reference (i.e. control cohort). Appropriate correlation structure will be chosen based on the data and clinical rationale.

The propensity score is defined as the probability of a patient receiving OAC/DOAC treatment or being censored conditional on both time-dependent covariates (e.g., comorbidities) and time-independent baseline covariates (age, gender, race, and baseline value for each of the time-dependent variables). The list of variables included in the logistic model will be based on clinical rationale. The propensity score acts as a balancing score among the cohorts.

After calculating the propensity score, the distribution of the propensity scores will be reviewed.

Each patient's weight is equal to the inverse of the probability of their treatment option and censoring (weight=1/propensity score). The numerator of the weight is the propensity score that a patient is on observed treatment/censored in a time period conditional on the baseline covariates. Denominator of the weight is the same propensity score conditional on time-dependent (factors such as CHA2DS2-VASc score, history of bleeding, etc.) and time-independent confounders. If an ever-treated patient has a very low propensity score, a very large weight can be created. Large weights can increase the variability of estimated treatment effect. In order to address this, the weights will be stabilized. Stabilized weights for treatment and censoring will be calculated for each time period of a patient. This reduces the variability of the weights.

$$SW = \prod_{k=0}^{t} \frac{f[A(k) | \overline{A}(k-1), V]}{f[A(k) | \overline{A}(k-1), \overline{L}(k)]}$$

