The distribution of the stabilized weight will be reviewed. If no extreme outliers are observed, the stabilized weights will be applied to the sample. In cases of extreme outliers, the large weights could be set to a less extreme value (e.g. recoding all weights that are outside 5th and 95th percentile to the 5th and 95th value, respectively). If needed, truncation can be done after stabilizing the weights.

Pfizer Confidential

Page 29 of 37

Do not distribute for purposes outside of specific activities related to development of FDAMAs114 compliant pieces. Content within this protocol is subject to change based on communication planning and input by external review committees.

Apixaban NON-INTERVENTIONAL STUDY PROTOCOL

After the weights are applied, the balance of the time-dependent and time-independent covariates will be assessed.

First, the means and proportions of baseline variables will be compared. The standardized difference compares the difference in means in units of the standard deviation. If the standardized difference is less than 10%, the covariates will be considered balanced.

For continuous variables, the balance of the distribution will also be assessed. The high-order movements and interactions between variables should be similar between cohorts. The standardized difference will be used to compare the mean of the square of continuous variables. Graphical comparisons of the distribution of continuous variables will be completed. Side-by-side boxplots and empirical cumulative distribution functions will be used to the compare the distribution of continuous covariates in the unweighted and weighted samples. Since the graphical approach can be subjective, a numerical method for comparing the distribution of continuous baseline covariates will also be completed. Kolmogorov-Smirnov test allows a comparison of the distribution of a continuous variable between two independent groups.33.34.35.36

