# Time-Varying Cox Regression Models (Secondary Clinical Objectives)

Time-varying Cox models will be used to compare the time to stroke/SE, major bleeding, and death between: 1) treated vs untreated; 2) each OAC vs untreated after inverse probability treatment weighting. Treatment will be used as a time varying covariate, in order to account for the untreated period of an ever-treated patient. Weights generated using IPW will be incorporated.

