# Marginal Structural Models (MSMs; Secondary Cost Objective)

A weighted generalized estimating equation (GEE) models will be applied for the multivariate analysis of health care costs among: treated vs untreated; 2) each OAC vs untreated. For cost outcomes, gamma distribution and a log link will be used. IPW weights will be incorporated to adjust for baseline covariates and any time dependent confounders. Time-dependent confounders will not be included in the repeated measures model – as their effects have been incorporated into the weights. Treatment will be included as a time-dependent variable, and time-invariant covariates may be included based on results of IPW and clinical rationale.

All data analysis will be executed using the statistical software SAS version 9.4.

Do not distribute for purposes outside of specific activities related to development of FDAMAs114 compliant pieces. Content within this protocol is subject to change based on communication planning and input by external review committees.

Apixaban NON-INTERVENTIONAL STUDY PROTOCOL

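### The stabilized weights carry the baseline covariates in the numerator, so they cannot adjust for them, yet the Cox models name no baseline covariates and the cost GEE makes them optional

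*Protocol*

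**What the plan says.** All references are to the protocol; the SAP was not at hand.

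- **Weights (Section 8.7, Inverse Probability Weighting).** The numerator is the probability that a patient "is on observed treatment/censored in a time period conditional on the baseline covariates". For the denominator the text reads "Denominator of the weight is the same propensity score conditional on time-dependent" and adds the time-independent confounders. The printed formula agrees: V stands in the numerator and the covariate history L in the denominator. The same section describes the baseline set as "time-independent baseline covariates (age, gender, race, and baseline value for each of the time-dependent variables", so V is the whole baseline confounder set. Barring extreme outliers, the stabilized weights are the ones applied.
- **Purpose of the weights.** The data analysis paragraph of the abstract gives IPW the task of balancing the treatment cohorts. Section 8.7 then tests baseline variables after weighting: "If the standardized difference is less than 10%, the covariates will be considered balanced".
- **Cox models (Section 8.7, Time-Varying Cox Regression Models).** Treatment enters as a time-varying covariate, and "Weights generated using IPW will be incorporated". No baseline covariate is named.
- **Cost models (Section 8.7, Marginal Structural Models).** "IPW weights will be incorporated to adjust for baseline covariates and any time dependent confounders". On the model terms, "time-invariant covariates may be included based on results of IPW and clinical rationale".
- **Section 8.8.** A multivariable Cox regression is listed as a sensitivity analysis for the clinical outcomes.

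**The concern.** Putting V in the numerator is a recognised way to stabilize weights, but it carries a condition: V must then be in the outcome model. The protocol does not impose that condition. It says the weights themselves do the baseline adjustment.

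An analyst following the text would fit a weighted Cox model with treatment as the only covariate and report the result as IPW-adjusted, although differences in age, sex, race and baseline comorbidity between treated and untreated time had not been removed. The comparisons affected are stroke/SE, major bleeding and death, for any OAC and for each OAC analysed against no treatment.

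The protocol itself expects such differences. Section 6 suggests that older patients may go untreated because of short life expectancy, fear of bleeding and poor general health. If non-treatment follows poor prognosis in this way, an untreated group with worse baseline risk would make OACs look protective against death even with no true effect.

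**Working it through.** The protocol gives no figure to reproduce here. The check has an algebraic part, which needs no assumptions about effect sizes, and a simulation part, which does.

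**1. What the weights do.** At period k the weight contributes

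f[A(k) | past A, V] / f[A(k) | past A, V, history of L].

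The words of the protocol put both V and the time-dependent covariates in the denominator. Multiplying the actual treatment probability by this ratio gives the treatment probability in the weighted population:

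f[A(k) | past A, V, L] × f[A(k) | past A, V] / f[A(k) | past A, V, L] = f[A(k) | past A, V].

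L has dropped out and V has not: in the weighted population treatment still depends on V.

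The first period shows this most directly. V contains the baseline value of each time-dependent variable. If those variables still hold their baseline values at k = 0, numerator and denominator condition on the same information, the ratio is 1, and the initial treatment choice is not reweighted at all. The censoring weights are described in the same way.

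**2. Size, under stated assumptions.** Set-up: 30,000 patients, 16 intervals, 10 replicates per scenario; V standard normal; a time-varying L that depends on V and raises the log-odds of both treatment and event by 0.3 per unit; no effect of treatment on L or on the event, so the true HR is 1.00; no censoring modelled. The outcome model is a weighted pooled logistic regression, the discrete-time analogue of the Cox model. The first column gives the assumed log-odds of treatment and of event per SD of V.

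| Treatment / event | Crude HR | Protocol weights, treatment only | Protocol weights, V in model | V out of numerator, treatment only |
|---|---|---|---|---|
| -0.2 / 0.3 | 1.01 | 0.96 | 0.99 | 0.99 |
| -0.3 / 0.5 | 0.92 | 0.87 | 1.00 | 1.00 |
| -0.5 / 0.5 | 0.77 | 0.73 | 0.98 | 0.99 |
| +0.3 / 0.5 | 1.53 | 1.45 | 0.99 | 1.00 |
| 0 / 0.5 | 1.22 | 1.15 | 1.01 | 1.01 |

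In the last row V affects treatment only through L. In the first three rows the weighted HR lies further below 1 than the crude HR does, because L confounds in the opposite direction to V and the weights remove only L's part.

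Standardized difference of V between treated and untreated time:

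| Treatment / event | Unweighted | Protocol weights | V out of numerator |
|---|---|---|---|
| -0.2 / 0.3 | -0.08 | -0.08 | -0.01 |
| -0.3 / 0.5 | -0.23 | -0.22 | -0.01 |
| -0.5 / 0.5 | -0.49 | -0.49 | -0.02 |
| +0.3 / 0.5 | 0.59 | 0.59 | -0.01 |
| 0 / 0.5 | 0.19 | 0.19 | -0.02 |

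**3. A second simulation** used a binary baseline factor (initiation OR 0.45, event HR 2.5, both assumed) and one time-varying confounder, over 24 months in 8 runs of 60,000 patients, again with no true effect. Crude HR 0.71; protocol weights with treatment only, 0.76; either remedy, 1.00.

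**4. What the balance check would show.** The weights barely move the imbalance, so a covariate fails the 10% rule when its unweighted difference clearly exceeds 10% and passes when it does not. Four of the five scenarios fail. The first passes at 0.08 while its HR is 0.96.

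**The case against.** - **The weight formula is legitimate and the outcome covariates could be left to the SAP.** The first part is right: the formula is not wrong in itself, and the Cox section does not forbid baseline terms. But the protocol does more than stay silent. It states that the weights adjust for baseline covariates and calls the time-invariant terms optional. A SAP that follows this inherits the error; one that corrects it has to depart from the protocol.
- **The GEE may include the covariates.** This stands. A reader might infer that every treated-versus-untreated estimate stays confounded. The text does not support that for costs, because an analyst who sees imbalance may enter all of V.
- **The balance check would expose the problem.** Often it would, but the protocol gives no remedy for the Cox models. Truncation, the only change to the weights it offers, does not restore balance on V. Equally, a reader might infer that the check must fail by construction. It need not, as the first scenario shows.
- **The section also writes the weight as one over the propensity score.** Unstabilized weights would balance V, but the section goes on to stabilize the weights and to apply the stabilized version.
- **There are other safeguards.** The secondary objectives are optional and will be dropped if the predictors of treatment are judged profound (Section 8.7). A multivariable Cox model is planned as a sensitivity analysis (Section 8.8). Residual confounding is acknowledged and only associations are claimed (Section 8.10). The primary objective does not use these weights. All of this limits the reach of the problem, but none of it repairs the main secondary estimates if they are produced.

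**Conclusion.** The concern holds as a contradiction within Section 8.7: the weights are built so that they do not adjust for V, while the balance check and the cost section rely on them to do so and neither outcome model requires V. As specified, the main Cox estimates for stroke/SE, major bleeding and death keep baseline confounding. The GEE cost estimates do too, unless all of V is included.

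That conclusion rests on algebra. The size does not. With a true HR of 1.00, the assumed scenarios gave 0.96 under the weakest confounding and 0.73 to 1.45 across the set, so the direction as well as the amount depends on confounding strengths the documents do not give. No single figure should be read as the bias expected in this study. Because the comparisons concerned are the study's main clinical contrasts and the correction is cheap, it should be made before the secondary analyses are run.

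**What to change.** Choose one and state it in Section 8.7.

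**(a) Marginal version.** Condition the numerators for treatment and censoring on treatment history and time only. The weighted Cox and GEE models can then contain treatment alone, the statement that the weights adjust for baseline covariates becomes correct, and the 10% baseline check can stay, run on the weights as applied. Cost: somewhat more variable weights.

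**(b) Conditional version.** Keep V in the numerator and require every V covariate in both the Cox and the GEE models. Change the permissive wording on time-invariant covariates in the cost section to a requirement, and add the same requirement to the Cox section. Correct the statement that the weights adjust for baseline covariates. Replace the marginal baseline balance check with an assessment of the time-dependent covariates within levels of V. Cost: the estimate is conditional on V and should be reported as such.

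The two should not be mixed: checking baseline balance with (a)-type weights while analysing with (b)-type weights tests weights the analysis does not use. Either option needs a few sentences and minor programming, with no new data.

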#### Apixaban NON-INTERVENTIONAL STUDY PROTOCOL

- 4. Compare the risk of death among elderly patients treated versus untreated with OACs in the Medicare NVAF population.
- 5. Compare the all-cause health care costs among elderly patients treated versus untreated with OACs in the Medicare NVAF population.

**Study Design:** The study will be a longitudinal retrospective cohort analysis using the US Centers for Medicare & Medicaid Services (CMS) Medicare dataset from 01JAN2012-31DEC2016. The study will designate a 12-month baseline period prior to the identification period (01JAN2013-31DEC2016). This database only includes patients enrolled in fee-for-service (FFS) Medicare; those enrolled in managed-care plans will be excluded. Further, patient eligibility will be based on selection from the database according to the following inclusion and exclusion criteria (sections 2).

**Population:** Elderly patients (aged  $\geq 65$  years) will be required to have  $\geq 1$  inpatient or  $\geq 2$  outpatient medical claims (the 2 outpatient claims are  $\geq 7$  days apart) for AF during the identification period for the primary and secondary objectives. For the primary objective, two mutually-exclusive NVAF patient cohorts will be created: ever-treated with OAC and never-treated with OAC. For the secondary objective assessing clinical and healthcare utilization and costs, treatment status will be a time-varying covariate and ever-treated patients will contribute time-not-on-treatment to untreated effect.

For the primary and secondary objectives, the ever-treated with OAC population cohort will include newly diagnosed NVAF patients who ever initiated oral anticoagulant (OAC) treatment (apixaban, dabigatran, edoxaban, rivaroxaban, and warfarin) during the study period identified from 01JAN2013-31DEC2016. The never-treated with OAC population cohort will include newly diagnosed NVAF patients without any OAC claim from 01JAN2013-31DEC2016.

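### The Kolmogorov-Smirnov p-value named in section 8.7 is not calibrated for weighted data and at this scale flags differences the plan itself calls balanced; a descriptive weighted distance would serve better

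*Protocol*

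**What the plan says.** Protocol section 8.7, Inverse Probability Weighting, places the check after weighting: "After the weights are applied, the balance of the time-dependent and time-independent covariates will be assessed". It gives one numerical criterion: "If the standardized difference is less than 10%, the covariates will be considered balanced". For continuous variables it adds standardized differences of squared values, boxplots and empirical distribution functions. Because plots can be read subjectively, "a numerical method for comparing the distribution of continuous baseline covariates will also be completed". The method named is the two-sample Kolmogorov-Smirnov (KS) test: "Kolmogorov-Smirnov test allows a comparison of the distribution of a continuous variable between two independent groups". No weighted or clustered form is named, and no p-value cut-off is given.

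Three other statements bear on this:

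- The weights belong to patient time periods: "Stabilized weights for treatment and censoring will be calculated for each time period of a patient".
- In the secondary objectives (section 3, Population), "ever-treated patients will contribute time-not-on-treatment to untreated effect".
- In the cost model (section 8.7, Marginal Structural Models), "time-invariant covariates may be included based on results of IPW and clinical rationale".

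**The concern.** The KS p-value is derived for two independent samples in which each observation counts once. Here the check is made on weighted data. Depending on what is compared, a patient may also contribute many rows or appear in both groups. A p-value from the standard reference distribution then does not have its stated error rate.

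There is also a problem of scale. A test of equality answers whether any difference can be detected. Balance assessment asks whether the remaining difference is large enough to matter. In cohorts of many thousands these come apart, and the reader would see significant KS results beside covariates that pass the 10% rule, with no statement of which to believe.

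At stake is the clarity of the balance report, and indirectly the weighting results that the protocol lists as one basis for choosing cost-model covariates.

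**Working it through.** The protocol states no KS error rate or cut-off, so there is no figure to reproduce. Three checks were made at a nominal 5% with the asymptotic two-sample KS reference distribution. Checks A and B used 1,000 simulated data sets per setting, so a true 5% carries a simulation standard error of √(0.05 × 0.95 / 1000) = 0.7 percentage points.

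**A. Weighting, one row per patient, mutually exclusive groups.** Assumptions: 2,000 patients in total, one normal covariate, a log-odds slope on treatment of 0.5 or 1.0, and stabilized weights with a marginal numerator, so that weighting does balance the covariate.

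| Test | Slope 0.5 | Slope 1.0 |
|---|---|---|
| Unweighted KS | 100% | 100% |
| Weighted KS, known weights, nominal n | 7.0% | 11.0% |
| Weighted KS, known weights, effective n | 5.4% | 4.8% |
| Weighted KS, estimated weights, nominal n | 0.1% | 0.4% |
| Weighted KS, estimated weights, effective n | 0.0% | 0.0% |

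Effective n is (Σw)² / Σw². Run without weights, the test describes the sample before weighting. Run with weights, it rejects too often or too rarely depending on whether the weights are known or estimated. The protocol estimates its weights from logistic models. Substituting the effective sample size corrects only the known-weight case.

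**B. Comparison unit.** Assumptions: 1,000 patients, half ever treated, a random start month, treatment unrelated to the covariate, and all weights 1. There is therefore no imbalance to find.

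- Treated versus untreated person-months, with the baseline value repeated on each row: 68% rejection with 6 months of rows, 94% with 12, and 99.8% with 24.
- Ever-treated versus never-treated, one row per patient: 4.8%.

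So the independence problem is severe on the first unit and absent on the second.

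**C. Sensitivity at the protocol's scale.** Section 8.5 gives 11,837 patients per group for major bleeding. This part assumes independent, unweighted, normal groups with equal SD, so it needs nothing from A or B.

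- Critical distance: 1.358 × √(2 / 11,837) = 0.0177.
- Distance produced by a mean shift of d SD: 2Φ(d/2) − 1. This is 0.0080 at d = 0.02, 0.0199 at d = 0.05 and 0.0399 at d = 0.10, or about 0.40 d.
- Shift at which this distance reaches the critical value: 0.0177 / 0.40 ≈ 0.044 SD, less than half the plan's 10% limit.
- Simulated rejection (300 data sets each): 24% at d = 0.02, 91% at d = 0.05, and 100% just below d = 0.10.

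**D. What these weights are built to balance.** Section 8.7 states: "The numerator of the weight is the propensity score that a patient is on observed treatment/censored in a time period conditional on the baseline covariates". The denominator conditions on baseline and time-dependent factors together. Baseline covariates in both parts largely cancel, so the stabilized weights are not designed to balance them; they need handling in the outcome model. The weights in A have a marginal numerator, which favours the KS check. With the protocol's weights, a KS comparison of baseline covariates can show imbalance that the design leaves in place.

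**The case against.** The strongest reply is that nothing hangs on this test. Section 8.7 declares balance on the standardized difference alone. KS supplements the plots and has no alpha, cut-off or consequence. This stands, and it is why the point is minor.

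Four stronger readings are tempting, and the document does not support them:

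- *KS decides whether the weights are accepted.* Section 8.7 ties applying the weights to extreme outliers in their distribution. Balance is assessed afterwards, and no re-weighting rule is attached.
- *KS contradicts the 10% rule.* There is no KS rule to contradict. The two can give discordant signals, and the protocol does not say how to read that.
- *The groups are certainly not independent.* The check covers baseline covariates and speaks of similarity between cohorts. The propensity cohorts are ever-treated and never-treated, which share no patients. With one row per patient, independence holds (4.8% in check B). That is not the treated-versus-untreated contrast of the Cox and cost models, however, and the protocol does not say which unit is meant.
- *The KS p-value makes the cost-model covariate choice arbitrary.* That choice rests on weighting results in general together with clinical rationale, not on KS.

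It may also be said that a weighted variant is detail for a statistical analysis plan, and that the secondary objectives are optional. But the protocol itself names the test and describes it for independent groups, so the objection is to a stated choice and not to an omission.

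**Conclusion.** The point holds as a minor one. The standard KS p-value is not interpretable as a balance check on weighted data. With mutually exclusive cohorts it is miscalibrated in a direction that depends on how the weights arise: 7% to 11% with known weights, and below 1% with estimated weights. With person-time groups it fails further, because patients can be on both sides and baseline values repeat. Apart from both problems, at 11,837 per group it rejects about 90% of 5% standardized differences.

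The percentages in A and B rest on assumed sample sizes, slopes and numbers of months; they show direction and rough size, not what this study would see. The result in C rests only on the 11,837 figure and normal covariates. That figure is a power-calculation requirement, not a planned cohort size. Section 8.10 says the full Medicare database will be used, so cohorts may be larger and the over-sensitivity greater.

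**What to change.** In section 8.7, Inverse Probability Weighting:

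1. Delete the KS significance test.
2. Report the weighted KS distance (the maximum gap between the weighted cumulative distributions) as a descriptive measure, with one row per patient per interval. State whether the comparison is currently treated versus untreated, or ever-treated versus never-treated.
3. Keep the 10% standardized difference, for the mean and the mean square, as the sole balance criterion.
4. State that neither a KS p-value nor a KS distance will be used to choose covariates for the cost model. Baseline covariates in the weight numerator should be handled in the outcome model, because these weights do not balance them.

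The cost is a wording change and minor programming, since the distance is already part of the test. The downside is that any limit placed on the distance would be only a convention.
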